2.3.2. Benefit Assessment

LN and IgAN are life-long diseases that lead to progressive loss of kidney function. As kidney function declines, patients may suffer the morbidity and mortality associated with advanced CKD, dialysis, and kidney transplant. While there has been some progress in terms of approved treatments for patients with LN with recent approval of belimumab in multiple regions and voclosporin in the US, there remains a large unmet need for novel interventions, particularly in patients who are at risk of progressive kidney disease. For patients with LN, current off-label immunosuppressive or cytotoxic therapies as well as recently approved drugs still provide inadequate clinical response (low rates of CRR and high risks of relapse) and are associated with significant side effects limiting their tolerability and long-term use. These side effects can lead to chronic diseases such as hypertension, osteoporosis, diabetes, obesity, and infertility. For patients with IgAN, patients with persistent proteinuria despite treatment with ACE inhibitors and ARBs are particularly at risk of progression of kidney disease. Available data from IgA studies on the role of immunosuppressive therapy are not conclusive as most are relatively small and have limited follow-up ([Lai, 2016](#)). Development of new therapies targeting the underlying pathologic processes is critical to improving the care of patients with LN or IgAN.

Multiple sources of evidence suggest aberrant complement is a key mediator in the pathophysiology of LN and IgAN (Section [2.2](#)). Participants in the study may benefit from clinical improvement and decreased risk of kidney disease progression. Additionally, though ravulizumab is being tested as add-on treatment to allowed concomitant therapy consistent with the standard of care, in patients with LN there is potential for a less intensive course of background immunosuppression and improved safety profile.

2.3.3. Overall Benefit: Risk Conclusion

There is a high unmet need for effective therapies for patients with LN or IgAN because clinical outcomes are poor with the currently available standard of care. Given the cumulative data on the role of complement in LN and IgAN disease progression, the potential risks of ravulizumab are justified by the anticipated clinical benefits.

3. OBJECTIVES AND ENDPOINTS

3.1. Overview of Objectives and Endpoints

Objectives	Endpoints
Primary (Both Cohorts)	
To evaluate the efficacy of ravulizumab compared with placebo to reduce proteinuria in adult participants with LN or IgAN	Percentage change in proteinuria from baseline to Week 26 (based on 24-hr urine collection[s] at each time point)
Secondary (Both Cohorts)	
To evaluate the efficacy of ravulizumab compared with placebo to improve measures of kidney function in adult participants with LN or IgAN	Percentage change in proteinuria from baseline to Week 50 (based on 24-hr urine collection[s] at each time point)
	Percentage of participants with > 30% and > 50% reduction in proteinuria at Week 26 and Week 50 compared to baseline (based on 24-hr urine collection[s] at each time point)
	Change from baseline in eGFR at Week 26 and Week 50
	Absolute values and change from baseline in serum C3 and C4 concentrations at Week 26 and Week 50
Secondary (LN Cohort Only)	
To evaluate the efficacy of ravulizumab compared with placebo to improve measures of kidney function in adult participants with LN	Percentage of participants meeting the criteria for CRR at Week 26 and Week 50 (as defined in Section 3.2.5)
	Percentage of participants meeting the criteria for PRR at Week 26 and Week 50 (as defined in Section 3.2.5)
	Time to UPCR < 0.5 g/g as measured by spot urine sample
	Percentage of participants achieving corticosteroid taper to 7.5 mg/day at Weeks 14, 26, and 50
	Percentage of participants with Renal Flare (as defined in Section 3.2.1) through Week 50
	Percentage of participants with Extrarenal SLE Flare (as defined in Section 3.2.2) through Week 50
	Percentage of participants with Treatment Failure (as defined in Section 3.2.4) through Week 50
	Percentage of participants with Suboptimal Response (as defined in Section 3.2.3) through Week 50
	Absolute values and change from baseline in serum albumin at Week 26 and Week 50

Objectives	Endpoints
Secondary (IgAN Cohort Only)	
To evaluate the efficacy of ravulizumab compared with placebo on measures of kidney function in adult participants with IgAN	Percentage of participants meeting the criteria for Partial Remission at Week 26 and Week 50 (as defined in Section 3.2.6)
PK/PD/Immunogenicity (Both Cohorts)	
To characterize the PK/PD of ravulizumab in adult participants with LN or IgAN	Absolute values and change from baseline in total C5 and free C5 concentrations over time
	Absolute values and change from baseline in ravulizumab concentrations over time
To characterize the potential for immunogenicity of ravulizumab in adult participants with LN or IgAN	Incidence of ADAs over time
Safety (Both Cohorts)	
To characterize the safety and tolerability of ravulizumab in adult participants with LN or IgAN	Incidence of AEs and SAEs over time
Exploratory (Both Cohorts)	
To evaluate the efficacy of ravulizumab compared with placebo on hematuria in adult participants with LN or IgAN	Effect on hematuria as measured by 
Absolute value and change from baseline in RBC in urine from baseline to Week 26 and Week 50Percentage of participants with < 10 RBC/hpf
To assess quality of life based on participant-reported outcomes in adult participants with LN or IgAN based on treatment with ravulizumab compared with placebo	Change from baseline in SF-36 at Week 26 and Week 50
	Change from baseline in EQ-5D-5L at Week 26 and Week 50
To evaluate complement and autoimmune biomarkers in adult participants with LN or IgAN	Absolute values and change from baseline in levels of biomarkers in blood, urine, and kidney tissue at Week 26 and Week 50
Exploratory (LN Cohort Only)	
To assess the efficacy of ravulizumab in exploratory efficacy endpoints	Time to CRR and PRR (using spot UPCR)
	Percentage of participants with Overall Renal Response at Week 26 and Week 50 (CRR and PRR)
	Time to UPCR > 50% decrease from baseline (using spot UPCR)
To assess quality of life based on participant -reported outcomes	Change from baseline in FACIT-Fatigue score at Week 26 and Week 50

Objectives	Endpoints
To assess the efficacy of ravulizumab in other exploratory endpoints	Absolute values and change from baseline in anti-dsDNA and anti-C1q antibodies at Week 26 and Week 50
	Histology changes from baseline to Week 50
Exploratory (IgAN Cohort Only)	
To assess the efficacy of ravulizumab in exploratory efficacy endpoints	Slope of eGFR computed from baseline to Week 26 and Week 50

Abbreviations: ADA = antidrug antibody; AE = adverse event; C3, C4, C5, and C1q = complement components 3, 4, 5, and C1q; CRR = complete renal response; dsDNA = double-stranded DNA; eGFR = estimated glomerular filtration rate; EQ-5D-5L = EuroQoL 5-Dimensions 5-Level; FACIT = Functional Assessment of Chronic Illness Therapy; IgAN = immunoglobulin A nephropathy; LN = lupus nephritis; PD = pharmacodynamics; PK = pharmacokinetics; PRR = partial renal response; RBC = red blood cell; SAE = serious adverse event; SF-36 = Short Form (36) Health Survey; SLE = systemic lupus erythematosus; UPCR = urine protein to creatinine ratio

3.2. Definitions for Endpoints

3.2.1. Renal Flare (LN Cohort Only)

Renal Flare is determined in the opinion of the Investigator in addition to the criteria outlined below:

- For participants who achieve CRR (Section 3.2.5), a Renal Flare is the reproducible recurrence of proteinuria $\geq 1 \text{ g/g}$
- For all other participants, a Renal Flare is either of the following:
 - Reproducible increase of serum creatinine $> 25\%$ higher than baseline or above the upper limit of normal, plus any one of the following:
 - Reproducible proteinuria $\geq 75\%$ higher than baseline
 - Worsening active urinary sediment compared to baseline as defined by an increase of ≥ 5 red blood cells (RBCs)/ high power field (hpf) or new RBC casts (based on local laboratory results from at least 2 samples)
 - Kidney biopsy newly conducted since the biopsy used for eligibility demonstrating LN Class III or IV activity
 - Reproducible doubling of the UPCR from a 24-hour urine collection compared with the lowest previous value obtained after the first dose of study drug.
- **Reproducibility of proteinuria** requires that the proteinuria based on a UPCR from a morning spot urine collection is confirmed by UPCR calculated on a 24-hour urine collection obtained within a 2-week period.
- **Reproducibility of serum creatinine** requires 2 blood tests within a 2-week period.

Participants who meet criteria for the protocol-defined Renal Flare will receive additional standard of care therapy (as defined in Section 6.6). The Medical Monitor should be notified of the Renal Flare by the Investigator or Sub-investigator.

Any renal flare that does not meet the protocol-defined Renal Flare criteria may be treated with a limited duration of increased oral corticosteroids (< 14 days) after discussion with the Medical Monitor. Such treatment will not be considered additional standard of care therapy and will not be considered Treatment Failure.

Renal Flare criteria will be recorded on the Renal Flare case report form (CRF).

3.2.2. Extrarenal Systemic Lupus Erythematosus Flare (LN Cohort Only)

Extrarenal SLE Flare is defined as an increase in Systemic Lupus Erythematosus Disease Activity Index Safety of Estrogen in Lupus Erythematosus National Assessment (SELENA) Modification (SLEDAI-2K) ≥ 4 points (see Section 8.9.2 and Section 10.12) that is not accounted for by proteinuria, hematuria, urinary cellular casts, hypocomplementemia, or an increase in anti-double-stranded DNA (anti-dsDNA) antibody level.

Participants in the LN cohort who meet the criteria for Extrarenal SLE Flare may receive additional standard of care therapy, if considered clinically appropriate by the Investigator (as defined in Section 6.6). If additional standard of care therapy is administered, the event is considered a Severe Extrarenal SLE Flare.

Participants will be allowed to receive a limited number of corticosteroid treatments for non-severe extrarenal SLE flare, if clinically warranted as outlined below. Such treatment will not be considered additional standard of care therapy and will not be considered Treatment Failure.

- Up to 2 corticosteroid treatments will be allowed for a non-severe extrarenal SLE flare.
 - One corticosteroid treatment will be allowed between Week 12 (end of steroid taper) and Week 22 (4 weeks prior to Week 26 primary endpoint).
 - One corticosteroid treatment will be allowed between Week 26 and Week 46 (4 weeks prior to final analysis).
- Each treatment course should be no longer than 14 days in duration with the steroid dose returning to 7.5 mg/day by Day 14.
- Up to a total of 20 mg/day (prednisone or prednisone equivalent) is permitted.
- There can be no concurrent worsening of renal disease (as defined by the criteria for a Renal Flare).

3.2.3. Suboptimal Response (LN Cohort Only)

A Suboptimal Response is determined in the opinion of the Investigator in addition to the following criteria after the Week 26 Visit:

- Reproducible proteinuria $\leq 25\%$ decreased compared to baseline based on UPCR on a 24-hour urine collection performed by the central laboratory

Reproducibility of proteinuria requires that the proteinuria based on a UPCR from a spot urine collection is confirmed by a central laboratory UPCR calculated on a 24-hour urine collection obtained within a 2-week period.

Participants with Suboptimal Response must be discussed with the Investigator and Medical Monitor. Participants with Suboptimal Response will stay in the study and continue to receive study drug. Intensification of current standard of care or introduction of new immunosuppressive therapies are allowed per the clinical discretion of the Investigator in conversation with the Medical Monitor and will be considered additional standard of care therapy.

Participants with Suboptimal Response will be included as Treatment Failure.

3.2.4. Treatment Failure (LN Cohort Only)

Treatment Failure is defined as the occurrence of any of the following events:

- Receipt of additional standard of care therapy (as defined in Section [6.6](#)) at any time up to Week 50 for protocol-defined Renal Flare, Severe Extrarenal SLE Flare, or Suboptimal Response

Increase in corticosteroids for extrarenal SLE flare not meeting the protocol definition of Severe Extrarenal SLE Flare, renal flare not meeting protocol definition for Renal Flare, lack of response not meeting the protocol definition for Suboptimal Response, other medical conditions or surgery limited to ≤ 14 days duration are **not** included in Treatment Failure.

Participants who meet the criteria for Treatment Failure may continue to receive the study medication and stay in the study.

3.2.5. Complete and Partial Renal Response (LN Cohort Only)

CRR and partial renal response (PRR) will be assessed at Week 26 and Week 50.

To achieve CRR ([Rovin, 2019](#)), participants in the LN cohort must meet all 3 of the following criteria:

- A decrease in mean UPCR to ≤ 0.5 g/g based on two 24-hr urine collections obtained within 2 weeks prior to the study visit (Week 26 or Week 50)
- $eGFR > 60$ mL/min/1.73 m² or no $eGFR$ reduction $\geq 20\%$ from the baseline value based on the mean of 2 values. The first $eGFR$ value must be obtained within 2 weeks prior to the study visit (Week 26 or Week 50) and the second $eGFR$ value will be obtained on the study visit (Week 26 or Week 50).
- No Treatment Failure (as defined in Section [3.2.4](#))

To achieve PRR ([Rovin, 2019](#)), participants in the LN cohort must meet all 3 of the following criteria:

- A decrease in UPCR $> 50\%$ compared to the baseline value based on the mean of two 24-hr urine collections obtained within 2 weeks prior to the study visit (Week 26 or Week 50)
- $eGFR > 60$ mL/min/1.73 m² or no $eGFR$ reduction $\geq 20\%$ from the baseline value based on the mean of 2 values. The first $eGFR$ value must be obtained within 2 weeks

prior to the study visit (Week 26 or Week 50) and the second eGFR value will be obtained on the study visit (Week 26 or Week 50)

- No Treatment Failure (as defined in Section 3.2.4)

3.2.6. Partial Remission (IgAN Cohort Only)

Partial Remission will be defined as mean proteinuria < 1 g/24-hrs based on 2 valid 24-hr urine collections obtained within 2 weeks prior to the study visit (Week 26 or Week 50).

4. STUDY DESIGN

4.1. Overall Design

This is a Phase 2, randomized, double-blind, placebo-controlled, multicenter study of ravulizumab in addition to allowed concomitant therapy consistent with the standard of care in adult participants (18 to 75 years of age) with either LN or IgAN. All participants must be naive to complement inhibitor treatment and have either a diagnosis of LN with an active flare or IgAN based on kidney biopsy, eGFR ≥ 30 mL/min/1.73 m², and proteinuria [defined as UPCR ≥ 1 g/g from one 24-hr urine collection (LN cohort) or as mean protein ≥ 1 g/24-hr from 2 valid 24-hr collections (IgAN cohort)]. Participants in the IgAN cohort must have been treated with stable doses of the maximum tolerated RAS-inhibiting medications and have controlled, stable blood pressure ($< 140/90$ mmHg) for ≥ 3 months prior to Screening.

The study consists of an up to 6-week Screening Period, a 26-week Initial Evaluation Period, a 24-week Extension Period, and a 36-week post-treatment Follow-up Period. Thus, the total treatment duration is 50 weeks and the total study duration is up to 86 weeks.

Participants will be screened for eligibility for up to 6 weeks during the Screening Period. Approximately 120 adult participants with either LN or IgAN will be enrolled into the study. For each disease cohort, 60 participants will be randomly assigned in a 2:1 ratio to receive ravulizumab or placebo (40 ravulizumab, 20 placebo). Randomization will be stratified by whether corticosteroid induction treatment was initiated prior to Screening versus during the Screening Period for participants in the LN cohort and by mean proteinuria (1 to 2 g/day versus > 2 g/day) from 2 valid 24-hr urine collections during the Screening Period for participants in the IgAN cohort.

For participants in the LN cohort, all screening laboratory assessments should be performed as soon as possible after signing of the informed consent form (ICF). All participants in the LN cohort should be randomized as soon as possible once eligibility is confirmed.

All participants are required to have meningococcal vaccination; however, for participants in the IgAN cohort, every effort should be made to start the meningococcal vaccination series at least 14 days prior to randomization in order to avoid antibiotic prophylaxis and minimize the potential triggering of innate immunity with possible effects on proteinuria and hematuria.

During the Initial Evaluation Period, all participants will receive a weight-based loading dose of ravulizumab or placebo on Day 1, followed by weight-based maintenance doses of ravulizumab or placebo on Day 15 and then q8w thereafter ([Table 8](#)). All participants will receive allowed concomitant therapy consistent with the standard of care for participants with LN and IgAN throughout the study as defined in Section [6.5](#).

During the 24-week Extension Period, participants will continue to receive study drug (ravulizumab or placebo):

- Participants in the LN cohort will continue to receive their randomized allocation of study drug (ravulizumab or placebo) q8w until the end of the Extension Period. Participants will receive additional standard of care therapy in the event of a protocol-defined Renal Flare or Severe Extrarenal SLE Flare. Additional standard of care

therapy for participants with Suboptimal Response is allowed at the clinical discretion of the Investigator in conversation with the Medical Monitor.

- Participants in the IgAN cohort randomized to the placebo group will switch to receive a blinded loading dose of ravulizumab at Week 26 and then open-label weight-based dosing of ravulizumab q8w until the end of the Extension Period.
- Participants in the IgAN cohort randomized to the ravulizumab group will receive a blinded dose of 900 mg ravulizumab at Week 26 and then open-label weight-based dosing of ravulizumab q8w until the end of the Extension Period.

During the 36-week Post-treatment Follow-up Period, participants will continue to receive standard of care, at the discretion of the Investigator, and will be monitored for safety, clinical events of interest, and kidney function.

Participants who discontinue study drug early and agree to remain in the study should continue to attend their scheduled protocol visits until Week 50. During these visits, all assessments except for study drug administration should be performed according to the Schedule of Assessments.

Participants who withdraw from the study will be followed for safety until 8 weeks after the last dose of study drug.

The end of study is defined as the last participant's last visit in the Post-treatment Follow-up Period.

To ensure the adequacy of the dose regimen, an interim PK/PD analysis for dose confirmation will be conducted by an independent clinical pharmacologist (Section 9.5.1). The interim PK analysis will be conducted using masked PK/PD data from the first 10 participants treated with ravulizumab (a minimum of 3 participants in each disease-specific cohort). In the event of dose adjustments, the participants treated with the previous dose will switch over to the new dose and continue treatment on study but will be excluded from the primary efficacy analysis.

Replacement participants may be enrolled to preserve study power.

4.2. Scientific Rationale for Study Design

A randomized, double-blind, placebo-controlled study design is selected to provide the most robust evidence of the efficacy of ravulizumab on clinical response, disease progression, and safety. Randomization minimizes the effects of baseline differences and confounding factors on the study endpoints. The use of a placebo comparator allows for the analysis of the true treatment effect of ravulizumab by minimizing the risk of selection bias. An unequal randomization scheme was chosen to decrease the number of participants receiving placebo. A single randomization stratum was selected for each cohort to ensure equal distribution of baseline characteristics that may impact the endpoints. The 50-week treatment duration provides adequate time to assess the safety and efficacy endpoints to demonstrate proof of concept for both cohorts in a Phase 2 study.

The standard of care allowed concomitant therapies employed in this protocol are consistent with recent clinical studies in patients with LN ([Rovin, 2019](#)) and IgAN ([Rauen, 2015](#)).

4.2.1. Rationale for Primary Endpoint

The primary endpoint for the study is percent change from baseline to Week 26 in 24-hr proteinuria.

Change in proteinuria is considered a valid surrogate endpoint for kidney survival in glomerular diseases. Change in proteinuria is also an acceptable endpoint for clinical studies as concluded during a scientific workshop facilitated by the National Kidney Foundation in collaboration with FDA and EMA in 2018 ([Coresh, 2019](#)). A decline in proteinuria in response to treatment is a strong predictor of kidney survival ([Hebert, 2001](#); [Wilmer, 2003](#)) and a > 20% relative treatment effect over standard of care in change in proteinuria is considered clinically relevant ([Holtkamp, 2020](#); [Levey, 2020](#)). Changes in proteinuria become evident before traditional markers of kidney survival (eg, ESRD, dialysis, or transplant); thus, it is especially useful to detect signs of efficacy for a proof-of-concept study. Accordingly, the effect of ravulizumab on the percentage reduction of proteinuria at Week 26 compared to baseline was selected as the primary endpoint for this study. It is expected that 26 weeks of treatment with ravulizumab will provide participants who respond to complement inhibition sufficient time to achieve reduction of proteinuria.

The gold standard for measuring proteinuria is a complete 24-hr urine collection.

Proteinuria is further justified in this Phase 2 study because of the role of active inflammation in both diseases leading to proteinuria as a clinical manifestation of active inflammation in the kidney. Ravulizumab has potent and rapid onset of anti-inflammatory effects that may be demonstrated through changes in proteinuria. Proteinuria may also result from irreversible scarring of renal tissue. Therefore, the presence of potentially reversible and active inflammatory kidney disease is ensured by requiring hematuria in participants with IgAN, and active class III or IV LN on kidney biopsy in participants with LN. Additionally, relatively preserved renal function with eGFR > 30 mL/min/1.73 m² is required for both disease cohorts.

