5.1.3. Inclusion Criteria Specific for IgAN Cohort

Disease Characteristics

13. Established diagnosis of primary IgAN based on kidney biopsy obtained any time prior to or during the Screening Period
14. Mean proteinuria ≥ 1 g/day on 2 complete and valid 24-hour urine collections during the Screening Period (Section [8.2.1](#))
15. For participants with a kidney biopsy used for eligibility > 1 year prior to Screening:
 - Presence of hematuria as defined by a positive result on urine dipstick for blood or ≥ 10 RBC/hpf microscopy on urine sediment as documented by the local laboratory. Presence of hematuria documented by the central laboratory may also be acceptable.
16. Compliance with stable and optimal dose of RAS inhibitor treatment including maximum allowed or tolerated ACE inhibitor and/or angiotensin receptor blocker dose for ≥ 3 months prior to Screening with no expected change in dose during the study (participants with established intolerance to RAS inhibitors may be included).
17. Controlled and stable blood pressure over the past 3 months $< 140/90$ mmHg

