5.4.6. Time to UPCR $\leq 0.5 \text{ g/g}$ (LN Cohort Only)

For the LN cohort, time to UPCR $\leq 0.5 \text{ g/g}$ will be summarized based on spot urine samples. Participants will be assigned as responders at the time of achievement of UPCR $\leq 0.5 \text{ g/g}$ or censored at the earliest of their treatment discontinuation time, receipt of additional standard-of-care therapy, study withdrawal, or death or at Week 50 if they have not responded or received additional standard-of-care therapy by then. Participants with baseline spot UPCR $\leq 0.5 \text{ g/g}$ will be excluded from the analysis.

A Kaplan-Meier cumulative distribution curve will be generated for treatment group, and a log-rank test comparing the curves will be performed. The corresponding summary table will present by treatment group the cumulative distribution function (CDF) estimate, the number of participants at risk, the number of participants responding, and the number of participants censored at each postbaseline time point. The table will also present the first quartile, median, and third quartile, along with 2-sided 95% CI, of time to UPCR $\leq 0.5 \text{ g/g}$.

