5.5.1. Effect on Hematuria

The effect on hematuria will be summarized by category of RBCs in urine.

The RBCs in urine will be summarized at each time point by treatment group using frequency statistics for categorical variables.

In addition, the percentage of participants with < 10 RBCs will be summarized at each scheduled visit by calculating the point estimate and 2-sided 95% CI, based on exact confidence limits using the Clopper-Pearson method.

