6.5. Appendix 5: Changes to Protocol-planned Analyses

Based on actual data received from the central laboratory, the RBCs in urine is categorical data. Hence, the endpoint of hematuria will be analyzed as a categorical variable instead of a continuous variable.

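### SAP 5.5.1 does not link hematuria results to each participant's baseline, so participants who enter and stay below 10 RBC/hpf dilute the planned percentage in both arms

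*Protocol*

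**What the plan says.** **The endpoint.** Protocol 3.1 and SAP 1.1 give two exploratory hematuria measures for both cohorts: the value and change from baseline in urine RBCs at Weeks 26 and 50, and the share of participants below 10 RBCs (per high-power field in the protocol).

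**The analysis.** SAP 5.5.1 states: "The RBCs in urine will be summarized at each time point by treatment group using frequency statistics for categorical variables". It adds the share below 10 RBCs at each scheduled visit with an exact 95% confidence interval. SAP 5.5 places this on the FAS and calls it descriptive. SAP 6.5 explains the move away from a continuous analysis: the central laboratory reports RBCs in categories. "Hence, the endpoint of hematuria will be analyzed as a categorical variable instead of a continuous variable". Nothing in SAP 5.5.1 replaces change from baseline.

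**Entry criteria.** Protocol 5.1.3 accepts an "Established diagnosis of primary IgAN based on kidney biopsy obtained any time prior to or during the Screening Period". Criterion 15 then applies only "For participants with a kidney biopsy used for eligibility > 1 year prior to Screening", and one way to meet it is "Presence of hematuria as defined by a positive result on urine dipstick for blood". The LN criteria in Protocol 5.1.2 do not mention hematuria or urinary sediment.

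**The rationale.** Protocol 4.2.1, defending proteinuria as the primary endpoint, says that "the presence of potentially reversible and active inflammatory kidney disease is ensured by requiring hematuria in participants with IgAN". For LN it relies on active class III or IV disease on biopsy.

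**The concern.** The stated objective is the effect of ravulizumab on hematuria. A percentage below a threshold at a visit mixes two groups: those who came down to it and those who were never above it. The second group carries no information about clearance but adds the same amount to both arms, which pulls the arms together. A chance imbalance between arms in baseline hematuria also passes directly into the percentages, and the placebo arm has only 20 participants per cohort.

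A within-participant comparison with baseline would separate the two groups. The protocol had one, as change from baseline. When RBCs became categorical, no categorical counterpart was written.

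What is at stake is how readable one exploratory endpoint is in a proof-of-concept trial. There is also a mismatch between a rationale sentence and an eligibility criterion.

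**Working it through.** The plan gives no hematuria rates, so there is no figure to reproduce. The check has a textual part and an illustration.

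**1. Who can enter below 10 RBC/hpf?**

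| Group | Hematuria required? | Can start below 10? |
|---|---|---|
| IgAN, eligibility biopsy 1 year old or less | No | Yes |
| IgAN, eligibility biopsy more than 1 year old | Yes: dipstick positive or at least 10 RBC/hpf | Yes, on dipstick alone |
| LN | No | Yes |

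**2. Effect on the percentage.** Let f be the share below 10 at baseline, s the share of those still below 10 at the visit, and p the share reaching below 10 among those at 10 or more at baseline.

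Reported percentage = f × s + (1 − f) × p

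With equal f and s in the two arms, the first term cancels, and the between-arm difference is (1 − f) × (p_rav − p_pbo).

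**3. Illustration.** Assumed: p = 60% on ravulizumab and 30% on placebo, s = 100%.

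| f | Ravulizumab | Placebo | Difference (points) |
|---|---|---|---|
| 0% | 60% | 30% | 30 |
| 10% | 64% | 37% | 27 |
| 25% | 70% | 47.5% | 22.5 |
| 50% | 80% | 65% | 15 |
| 75% | 90% | 82.5% | 7.5 |

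With s = 90% the differences are unchanged and the percentages are lower (at f = 50%: 75% versus 60%).

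**4. Precision.** Restricting to baseline hematuria enlarges the difference but loses participants. To weigh the two, take z = difference / √(p₁q₁/n₁ + p₀q₀/n₀), where q = 1 − p, with 40 and 20 participants and none missing. No test is planned; z serves only as a yardstick. The squared ratio of the two z values is the equivalent gain in sample size.

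- f = 50%, FAS: 0.15 / √(0.80×0.20/40 + 0.65×0.35/20) = 0.15/0.124 = 1.21
- f = 50%, restricted (20 and 10): 0.30 / √(0.60×0.40/20 + 0.30×0.70/10) = 0.30/0.182 = 1.65. Gain: (1.65/1.21)² ≈ 1.86
- f = 70%, FAS (88% versus 79%): 0.09/0.105 = 0.86. Restricted (12 and 6): 0.30/0.235 = 1.28. Gain ≈ 2.2
- f = 30%, FAS (72% versus 51%): 0.21/0.132 = 1.59. Restricted (28 and 14): 0.30/0.154 = 1.95. Gain ≈ 1.5

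**5. Chance imbalance.** Suppose there is no drug effect and 30% clear in both arms. If 40% of one arm and 60% of the other have 10 or more at baseline, the percentages are 0.60 + 0.40×0.30 = 72% and 0.40 + 0.60×0.30 = 58%, a spurious 14 points. With a true prevalence of 50% and 40:20 participants, the chance of a baseline imbalance of 20 points or more in either direction is about 17%.

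**The case against.** Much of the case on the other side stands.

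- **The endpoint is modest.** It is exploratory and descriptive, with an interval per arm and no between-arm test. The z values above describe no planned analysis.
- **Baseline is not wholly absent.** Categories are tabulated at each time point, and Protocol Tables 1 and 2 schedule urine sediment at Screening and Day 1. A baseline imbalance may therefore be visible by arm. What is missing is the link within participants.
- **Some shifts are already planned.** SAP 5.6.3.1 covers urinalysis and plans shifts from baseline for results that can be classed against a normal range. These may include urine RBCs, but they use the Safety Set and normal-range classes, not the 10 RBC/hpf cut.
- **The SAP treats similar percentages alike.** Steroid dose at or below 7.5 mg/day (SAP 5.4.7) and anti-C1q below the lower limit of normal (SAP 5.5.9) are also not conditioned on baseline. SAP 5.4.6 does say that participants already at the UPCR threshold "will be excluded from the analysis", but that is a time-to-event endpoint, where such participants have no event to wait for. It is only a loose precedent.

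A reader might go further and infer that the endpoint labels participants without hematuria as successes, or that it cannot address its objective. The SAP uses neither success nor response for it; it reports a prevalence by visit. Dilution weakens that measure without making it uninformative.

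A reader might also take the 4.2.1 sentence as the source of the problem. That sentence defends the proteinuria endpoint, and correcting it would leave SAP 5.5.1 unchanged. Nor does LN contradict it, because for LN the section relies on biopsy class.

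**Conclusion.** The gap is real but small in consequence. SAP 5.5.1 contains no analysis of change in hematuria within participants, although the protocol and the SAP's own endpoint table promise one. The percentage below 10 RBCs includes participants who never had hematuria at that level.

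The difference between arms shrinks by the share who start and stay below 10. It goes from 30 to 15 points in the example, and restricting to baseline hematuria is worth about 1.5 to 2.2 times the sample size when 70% to 30% have 10 or more at baseline. These sizes rest on assumed prevalence and clearance, on everyone who starts below 10 staying there, and on no missing data. The direction needs only that some participants start and stay below 10, with similar shares in both arms.

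Separately, the unconditional wording of 4.2.1 on IgAN does not match criterion 15. This touches the stated rationale for the primary endpoint but not its analysis. No primary or secondary analysis is affected.

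**What to change.** In SAP 5.5.1:

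1. Add a shift table of baseline RBC category by post-baseline category, by arm, at Weeks 26 and 50, as the categorical form of change from baseline. SAP 5.5.9 already uses this format for anti-dsDNA.
2. Add the percentage reaching below 10 RBC/hpf among participants with 10 or more at the last pre-dose central result.
3. Keep the FAS percentage beside it. Replacing it would be a trade-off, because the restricted figure drops new or worsening hematuria.
4. For Week 50 in IgAN, state which baseline applies, since placebo participants switch to ravulizumab at Week 26 and SAP 5.1.2 redefines baseline for that period.

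In the protocol, reconcile the 4.2.1 sentence on hematuria in IgAN with criterion 15.

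The cost is one SAP paragraph, a small amount of extra tabulation from data already collected, and one corrected protocol sentence. The added percentage will have a small denominator: 20 versus 10 participants if half have 10 or more at baseline, and 12 versus 6 if 30% do. Its intervals will be wide and should be read with the shift table.
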